9.5 Study size

Based on an incidence rate of VTE of 131.5 per 100,000 person-years and assuming that 18.6% of VTEs are associated with active cancer (1) and that 50% of patients with CAT have a recording for DOACs or LMWH within 30 days after initial VTE, we expect our cohort to include approximately 5,600 patients with CAT. Assuming a mean follow-up of 0.6 years following first CAT (according to the high mortality risk in these patients and the restriction to the first year following CAT) and incidence rates of 11.8 VTE recurrences, 14.4 significant bleeds and 80.0 deaths from any cause per 100 person-years, we expect to identify approximately 390 VTE recurrences, 480 significant bleeds and 2670 deaths from any cause within the first year after CAT. Based on the matching related fixed proportion of DOAC to LMWH users in our study cohort and the numbers mentioned above, this study would detect a significant difference between DOAC and LMWH users with 5% significance level and a power of 80% if the estimated HR is lower than 0.75, 0.77 or 0.89 respectively for VTE recurrence, serious bleeding or death from any cause. This is consistent with the HR of recurrent VTE ≤ 0.43 (supported by SELECT-D [14] and Costa et al. [15]) or with a more conservative HR (HR=0.71) as seen in the Hokusai VTE cancer trial for edoxaban (DOAC) compared to dalteparin (LMWH) [16].

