9.3.2 Outcomes definition

The study outcomes will be defined based on Read codes and ICD-9/10-CM diagnosis and procedure codes or laboratory, vital sign and other patient observation results.

Algorithms for the definition of recurrent VTE and of the bleeding events have previously been developed and refined using all information available in CPRD, HES and Office of National Statistics ONS [4, 8].

A random sample of identified potential VTE recurrences and significant bleeding events will be manually reviewed by utilizing patient summaries/profiles including HES APC, HES Outpatient, ONS death registration data (DRD) and PCP recorded symptoms, signs, laboratory tests, diagnostic and therapeutic procedures, medication use, discharge diagnoses, and cause of death to confirm the that outcomes have been appropriately identified.

Primary outcomes

- The risk of recurrent VTE at 3-months
- Composite of any major bleeding or clinically-relevant non-major bleeding-related hospitalization (per the ISTH criteria [9, 10] for identification of bleeding-associated hospitalizations) at 3-months
- All-cause mortality at 3-months

Secondary outcomes

- Recurrent VTE at 6- and 12-months post-index VTE

- Composite of any major or clinically-relevant nonmajor bleeding-related hospitalization at 6- and 12-months post-index VTE, including:
 - Intracranial hemorrhage (ICH)
 - Critical organ bleeding (e.g., intracranial, intraspinal, intraocular, retroperitoneal, intraarticular or pericardial bleeding or intramuscular with compartment syndrome)
 - Extracranial bleeding-related hospitalizations (including trauma-related)
- Composite of any major bleeding or clinically-relevant non-major bleeding-related hospitalization (per the ISTH criteria [9, 10] for identification of bleeding-associated hospitalizations) at 6 and 12-months
- Intracranial hemorrhage (ICH), critical organ bleeding and extracranial bleeding-related hospitalizations as separate outcomes
- All-cause mortality at 6- and 12-months
- Incidence rates of recurrent VTE, any clinically-relevant bleeding-related hospitalization and all cause-mortality in rivaroxaban, DOAC and LMWH patients experiencing CAT regardless of the bleeding risk associated with cancer type
- Duration of anticoagulation treatment and rivaroxaban, DOAC and LMWH discontinuation rates at 3-, 6-, 12-months and all available follow-up

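### The only power statement in section 9.5 rests on first-year events, but all three primary outcomes are set at 3 months, where power at the stated hazard ratios is about 42-46% on the plan's own rates

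*Protocol*

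**What the plan says.** Protocol section 9.5 gives one study-size calculation. It takes a cohort ("we expect our cohort to include approximately 5,600 patients with CAT") and a mean follow-up ("Assuming a mean follow-up of 0.6 years following first CAT"), which it justifies by high mortality and by "the restriction to the first year following CAT". It applies rates of 11.8, 14.4 and 80.0 per 100 person-years for recurrent VTE, significant bleeding and death. The result is: "we expect to identify approximately 390 VTE recurrences, 480 significant bleeds and 2670 deaths from any cause within the first year after CAT". It then says that the study would detect a difference between DOAC and LMWH users "with 5% significance level and a power of 80" per cent "if the estimated HR is lower than 0.75, 0.77 or 0.89 respectively for VTE recurrence, serious bleeding or death from any cause". It closes by calling this consistent with a recurrent-VTE HR of 0.43 or lower, or with a more conservative 0.71.

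Section 9.3.2 sets the horizon of the primary outcomes. The first is "The risk of recurrent VTE at 3-months", the second is the bleeding composite at the same time point, and the third is "All-cause mortality at 3-months". The 6- and 12-month versions of all three are listed as secondary. Section 8.1 names the primary outcomes without a time point, under an objective that spans 3, 6 and 12 months. Section 9.3.2 is therefore the only place that fixes the horizon.

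The protocol gives no 3-month event count, detectable HR or power.

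**The concern.** In a time-to-event comparison, power depends on the number of events inside the analysis window. Section 9.5 counts events over a year and the primary analyses stop at 3 months, so the primary analyses will have fewer events than the power statement uses.

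A reader who takes 80% power at 0.75, 0.77 and 0.89 as describing the primary outcomes would be misled about what a null 3-month result can exclude. This matters most for bleeding and death. Section 9.9 itself notes that a tendency to find the treatments similar is anticonservative in safety analyses.

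**Working it through.** **Inputs.** From section 9.5: 5,600 patients; mean follow-up 0.6 years; rates 0.118, 0.144 and 0.80 per person-year; 5% significance; 80% power; stated HRs 0.75, 0.77 and 0.89. From section 9.3.2: primary horizon 3 months (0.25 years). Two inputs are inferred because section 9.5 does not state them: a two-sided test and a 1:1 split. Together they reproduce the stated HRs.

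**Step 1. Reproduce the first-year events.** 5,600 × 0.6 = 3,360 person-years. Multiplying by the three rates gives 396, 484 and 2,688, against 390, 480 and 2,670 stated.

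**Step 2. Reproduce the stated HRs.** Schoenfeld's formula at 1:1 is HR = exp(−√(4K/d)), with K = (1.960 + 0.842)² = 7.849 and d the number of events.
- d = 390: HR 0.753
- d = 480: HR 0.774
- d = 2,670: HR 0.897

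Cut to two decimals, these are the stated 0.75, 0.77 and 0.89. Power at the stated HRs with the stated events is 81%, 82% and 85%. The calculation is sound, and it uses the full first-year count.

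**Step 3. Events by 3 months on the plan's rates.** With a constant death rate of 0.80 per year ending follow-up, mean follow-up to 3 months is (1 − exp(−0.80 × 0.25))/0.80 = 0.2266 years. 5,600 × 0.2266 = 1,269 person-years. Multiplying by the rates gives about 150 VTE recurrences, 183 bleeds and 1,015 deaths.

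**Step 4. Power at 3 months.** Power = Φ(½√d × |ln HR| − 1.960).

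| Outcome | Events, constant rates | Power at stated HR | HR detectable with 80% power |
|---|---|---|---|
| Recurrent VTE | 150 | 42% (HR 0.75) | 0.63 |
| Bleeding | 183 | 42% (HR 0.77) | 0.66 |
| Death | 1,015 | 46% (HR 0.89) | 0.84 |

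If nobody left follow-up before 3 months, events would be 165, 202 and 1,120, and power 46%, 46% and 50%.

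**Step 5. Front-loading.** The protocol gives no figure for how events spread over the year. Assume, for illustration only, that 50-60% of first-year events fall in the first 3 months:
- VTE: 195-234 events, power 52-60%, detectable HR 0.67-0.69
- Bleeding: 240-288 events, power 53-60%, detectable HR 0.70-0.72
- Death: 1,335-1,602 events, power 57-65%, detectable HR 0.86-0.87

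For 80% power at the stated HRs, Schoenfeld needs 380, 460 and 2,312 events. That is about 97%, 96% and 87% of the first-year totals within 3 months.

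**Step 6. A less favourable reading for this point: death.** A constant rate of 0.80 per year gives a mean first-year follow-up of (1 − exp(−0.80))/0.80 = 0.688 years, not 0.6. Suppose instead that death alone shortens follow-up to 0.6 years. The share dying is 2,670/5,600 = 0.477, and survivors contribute a full year, so the mean time to death among those who die is (0.6 − 0.523)/0.477 = 0.16 years. A truncated exponential with that mean puts about 79% of the deaths (about 2,100) within 3 months, which gives about 76% power at HR 0.89. Censoring for other reasons could equally explain the 0.6, so this is an upper scenario rather than an estimate.

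**Step 7. The VTE effects that section 9.5 cites.** At HR 0.71, 80% power needs 4 × 7.849/(ln 0.71)² = 268 events. Power is 92% with 390 events, 55% with 150, and 67-75% with 195-234. At HR 0.43, power with 150 events is above 99%.

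**The case against.** The strongest reply is that section 9.5 labels its horizon openly as the first year. A reader might infer that the protocol claims 80% power at 3 months, or adequacy for an HR of 0.71 at 3 months. It claims neither. Its arithmetic also reproduces. The defect is a mismatch of horizon and a missing figure for the primary outcomes, not a miscalculation. This stands, and the point is worded accordingly.

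A second reply is that front-loading could lift 3-month power. It could, but the protocol offers no share. Figures such as 65% power, or detectable HRs of 0.69, 0.72 and 0.87, rest on an assumption brought in from outside and should not be presented as following from the plan. For death the range is wider still, up to about 76%, if the 0.6 years is read as due to death alone. None of these scenarios reaches 80%.

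Third, the first benchmark that section 9.5 cites, an HR of 0.43 or lower, keeps more than 99% power at 3 months. A reader might infer that the primary VTE analysis is inadequate for every effect the plan has in mind. It is not: the shortfall concerns the stated detectable HRs and the conservative 0.71.

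Fourth, this is a retrospective cohort of existing records, so the calculation does not set enrolment. Results come with 95% confidence intervals, and section 7 plans a three-country meta-analysis to raise power. All true, and it limits the harm. It does not make a 12-month power figure informative about 3-month outcomes.

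Finally, the 1:1 split is inferred. The abstract expects at least three LMWH users per rivaroxaban user. At 1:3, even with all 5,600 patients kept, constant-rate power at the stated HRs falls to 33%, 33% and 36%.

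**Conclusion.** The point holds. The 80% power at 0.75, 0.77 and 0.89 applies to 12-month outcomes, which are secondary, and nothing in the protocol describes power for the 3-month primary outcomes. On the plan's cohort size and constant rates, with an inferred 1:1 split and two-sided 5% test, power at those HRs is about 42%, 42% and 46%, or at most 46%, 46% and 50% without attrition. Under the front-loading scenarios it is about 52-65%, and for death up to about 76%. The exact value depends on event timing that the protocol does not give; falling short of 80% does not, in any scenario examined. For recurrent VTE, the 3-month analysis is well powered for HR 0.43 and, on constant rates, not for HR 0.71 (about 55%).

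**What to change.** In section 9.5:
1. Label the HRs 0.75, 0.77 and 0.89, and the comparison with HR 0.71, as applying to the 12-month secondary outcomes.
2. Add the expected 3-month events and the detectable HR for each primary outcome. On the plan's constant rates these are about 150, 183 and 1,015 events and HRs of about 0.63, 0.66 and 0.84. State the allocation ratio and the sidedness of the test.
3. If events are expected to cluster early, state the assumed share and its basis, and show the results as a range.
4. Say that on those rates the 3-month VTE analysis is adequately powered for HR 0.43 but not for HR 0.71.

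The cost is a rewritten paragraph with less favourable figures. No extra patients or data are needed, and no analysis changes.

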9.6 Data management

- Raw and processed data files will be maintained by The Institute for Epidemiology, Statistics and Informatics (IfESI) on a secured network assessable server and made available only to members of IfESI's research team.
- IfESI and LIRN have developed standard definitions based on different medical and product dictionaries. All new code sets for hospital discharge diagnoses, in-hospital procedures, GP-recorded clinical diagnoses and prescribed medications and lab tests will be prepared by two physicians from

LIRN and IfESI. Existing and new code sets are reviewed for recentness, accuracy and completeness.

- Database management and analyses will be conducted using Stata 14 (StataCorp LP, College Station, Texas).

9.7 Data analysis

Baseline characteristics will be analyzed using descriptive statistics. Categorical data will be reported as percentages and continuous data as medians with accompanying 25%, 75% ranges or means \pm standard deviations (SDs). Descriptive analysis will be performed for each of the three distinct cancer cohorts listed above, namely, (1) the cohort of cancer patients without gastrointestinal and genitourinary cancers, (2) the cohort defined by the ISTH CAT guidelines (in acute CAT patients without a malignant neoplasm associated with a high risk of bleeding) and (3) an all cancer type cohort.

To adjust for potential confounding between the rivaroxaban (or DOAC) and LMWH cohorts, propensity scores will be calculated using a multivariable logistic regression model. The propensity score model will include commonly used variables and accepted risk factors for differential anticoagulation exposure identified at baseline including demographics, comorbidities, laboratory values, vital signs, other clinical observations and outpatient medication use (prescription and over-the-counter). All clinical characteristics listed in section 9.3.3 of this protocol will be included in the propensity score model. Propensity scores will then be used to assign weight to individual patients in the analysis using an overlap weighting approach. Overlap weighting assigns weights to patients that are proportional to their probability of belonging to the opposite treatment cohort. By design, overlap weighting results in the exact balance of all variables included in the propensity score model. This method of adjustment retains all patients in the dataset (unlike propensity score matching) and gives less weight to patients with extreme propensity scores (which is often a concern with inverse probability weighting).

Propensity scores will be estimated based upon commonly used variables and accepted risk factors for differential anticoagulation exposure identified during the baseline period including demographics, comorbidities, laboratory and vital signs and concurrent outpatient co-medication use. All clinical characteristics listed in section 9.3.3 of this protocol will be included in the propensity score model. Given the retrospective nature of the data analysis, the presence of a comorbid disease diagnosis will be identified based upon the recording of the specific comorbid read codes. Missing data for covariates will occur when an existing co-morbidity or co-medication is not recorded in the database. In such case we will assume that the respective patient did not suffer from the respective co-morbidity/did not use the respective co-

Reference Number: RD-SOP-1214
Supplement Version: 7

medication. Information on time varying variables e.g. BMI and smoking status will assumed to be constant unless a different variable entry is recorded. Whenever meaningful, missing data will be presented in separate categories labelled "not stated" or "unknown". No imputation will be performed for potentially missing outcomes/endpoint data. Separate propensity score models will be fit once for the primary analysis and for each subgroup analysis.

Propensity score matching operates by taking each treated study participant and finding the closest propensity score match among controls within a calliper (or bound). Conventional IPTW assigns a weight of $1/PS$ for treated and $1/(1 - PS)$ for untreated patients, allowing individuals with underrepresented characteristics to count more in the analysis. IPTW can produce inflated variance estimates which can be addressed through a simple stabilization of weights (multiplying propensity scores of each participant by the relative proportion of the specific cohort makes up of the total study population). In observational data, in which the initial differences in treatment groups may be large, these methods can modify the target population, fail to achieve good balance or substantially worsen precision. Overlap weighting assigns weights to each patient that are proportional to the probability of that patient belonging to the opposite treatment group. Specifically, treated patients are weighted by the probability of not receiving treatment ($1 - PS$) and untreated patients are weighted by the probability of receiving the treatment (PS). These weights are smaller for extreme PS values so that outliers who are nearly always treated (PS near 1) or never treated (PS near 0) do not dominate results and worsen precision, as occurs with IPTW. These outliers contribute relatively less to the result, while patients whose characteristics are compatible with either treatment contribute relatively more. The resulting target population mimics the characteristics. Overlap weighting also leads to exact balance on the mean of every measured covariate when the PS is estimated by a logistic regression. Like all PS-based methods, overlap weighting cannot adjust for patient characteristics that are not measured and included in the model for the PS. When initial imbalances in patient characteristics between treatment groups are modest, overlap weighting yields similar results to IPTW. The advantages of overlap weighting are greatest when comparator groups are initially very different. To test the robustness of our conclusions to various methods for confounding adjustment, we will also perform a number of sensitivity analyses e.g. *1:1* matching based on propensity scores.

Cox proportional hazards regression is a method for investigating the effect of variables upon the time a specified event takes to happen. We will fit Cox proportional hazards regression models (with robust estimators) to compare event rates over time for the rivaroxaban (or any DOAC) and LMWH cohorts in the Xarelto SmPC and CAT guidance cancer type cohorts. As propensity score based methods will be assumed to

Reference Number: RD-SOP-1214
Supplement Version: 7

balance key characteristics of the treatment cohorts, the only independent variable that will be included into Cox regression model will be anticoagulant received (rivaroxaban or DOAC or LMWH). Results of Cox regression will be reported as hazard ratios (HRs) with 95% confidence intervals (CIs).

We will use an intention-to-treat approach to analyze the data in which, patients will be evaluated based on the initial anticoagulant prescription registered and will be followed until endpoint occurrence, end-of-database activity, end of data availability or end of designated follow-up time (3-, 6- or 12-months), whichever comes first. Time from treatment initiation to end of follow-up will then be considered the time at risk. On-treatment analysis (patients will be followed until endpoint occurrence, end-of-database activity, end of data availability, end of designated follow-up time (3-, 6- or 12-months), anticoagulant discontinuation or switch, whichever comes first) will be performed as a sensitivity analysis. No adjustments for multiple hypothesis testing will be performed.

Subgroup analyses

Analysis of the recurrent VTE, any clinically-relevant bleeding-related hospitalization and all-cause mortality outcomes among patients prescribed with rivaroxaban and any DOAC (apixaban, dabigatran, edoxaban, rivaroxaban) versus patients prescribed with LMWH patients for acute CAT will be performed stratifying by cancer subtypes (specific subtypes dependent on available sample sizes). To limit the number of analyses performed (and the impact of multiple hypothesis testing), subgroup analyses will only be performed on the primary effectiveness and safety endpoints (recurrent VTE, any clinically-relevant bleeding-related hospitalization and all-cause mortality).

Further descriptive analyses

We will calculate incidence rates of recurrent VTE, any clinically-relevant bleeding-related hospitalization and all-cause mortality in rivaroxaban patients experiencing CAT regardless of the cancer type and associated bleeding risk. The duration of anticoagulation treatment and discontinuation rates at 3-, 6- and 12-months follow-up will be estimated based on instructions at prescriptions filled in CPRD.

Sensitivity analyses

Various sensitivity analyses will be performed to test the robustness of our study's conclusions. A sensitivity analysis will be performed whereby patients with cancer will need to be admitted to the hospital, emergency department or observation unit for acute DVT and/or PE on or after January 1, 2013 in order to better estimate the "contemporary" comparative effectiveness and safety of the two treatment cohorts/strategies. We will perform 1:1 propensity score matching of rivaroxaban and LMWH patients and

analyze data using a proportional hazards models for the subdistribution of competing risk (competing risk model) to compare event incidences over time for the cohorts. An “on-treatment” approach (patients censored at the first event, anticoagulant discontinuation or switch or end of data availability) will also be performed as the CPRD GOLD and Aurum EHR contain prescription instructions commonly used to identify continuous anticoagulation use. Analysis at 6 and 12-months will be performed.

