9.2.2 Study time frame

We will use CPRD GOLD and Aurum EHR data from January 1, 2013 through latest available data (currently March 2019).

- Patient identification period: The patient identification period will be restricted to January 1, 2013 through latest available data as shown in the figure above.
- Cohort entry: CAT diagnosis, hospitalization or emergency department admission or primary care visit with an incident VTE event.
- Index date: The date of first rivaroxaban (or any DOAC) or LMWH use according to registered prescription 7-30 days after CAT event (new-user design).
- Pre-index eligibility period: Patients will be required to have at least 12-months of EHR registration prior to the CAT event.
- Post-index eligibility period: There will be no minimum post-index eligibility requirement for patient identification.
- Follow-up period: There will be a minimum of 3 months and maximum 12-months follow-up period. Patients will be followed from the first recording of AC use (7-30 days after CAT event) until the end of eligibility.

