9.3.3 Covariate definition

Patient baseline characteristics such as age, gender, comorbidities, cancer-specific data and comedications will be collected at the index date or from the last recorded value within the baseline period. The presence of characteristics will be assessed from patients' medical and pharmacy data in the baseline period (see Annex 1).

Demographic characteristics

- Sex
- Age
- Race
- Individual DOAC or LMWH used to treat CAT
- Number of days between CAT and first recording of anticoagulation use

Clinical characteristics

- Presence of the following clinical characteristics will be assessed from patients' medical and pharmacy data in the baseline period:
 - **Comorbidities/prior history/risk scores:**
 - Number of days from January 1, 2013 to qualifying CAT diagnosis
 - Cancer type(s) present at CAT diagnosis
 - Metastatic disease at time of CAT diagnosis
 - Active/recent treatment (within 3-months pre- or post-CAT diagnosis)
 - Chemotherapy/immunotherapy
 - Radiation therapy
 - Surgical
 - Initial anticoagulation therapy on day of CAT diagnosis
 - Intracranial bleeding
 - Systemic embolism
 - Deep vein thrombosis
 - Pulmonary embolism
 - Heart failure
 - Hypertension
 - Ischemic stroke/transient ischemic attack
 - Peripheral vascular disease
 - Myocardial infarction
 - Percutaneous coronary intervention
 - Coronary artery bypass grafting
 - Any major bleed

- Major adverse limb events (need for surgical or endovascular revascularization or limb amputation)
- Gastrointestinal bleeding
- Central venous catheter
- Liver disease
- Coagulopathy
- Gastroesophageal reflux disease/heartburn
- Anemia
- Asthma
- Chronic obstructive pulmonary disease
- Sleep apnea
- Smoker
- Alcohol abuse
- Anxiety
- Depression
- Lower extremity paralysis
- Psychosis
- Osteoarthritis
- Diverticulitis
- Crohn's disease or ulcerative colitis
- Active or treated *Helicobacter pylori*
- Hypothyroidism
- Recent major surgery within 12 weeks of index event
- Dementia
- Recent trauma (with 90-days)

- Primary hypercoagulable state (e.g., activated protein C resistance, prothrombin gene mutation, antiphospholipid syndrome, lupus anticoagulant syndrome and other primary thrombophilia (per Read code; ICD-9 or -10 coding provided in Annex 1))
- Prior history of VTE
- Varicose veins
- Chronic venous insufficiency (per Read code or ICD-9 /-10 coding provided in Annex 1)
- Acute coronary syndrome
- Carotid stenosis
- Pneumonia
- Osteoporosis
- Orthopedic surgery

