- Rheumatoid arthritis/collagen vascular disease
- Proteinuria
- Ischemic (coronary) heart disease
- Number of hospitalizations for any cause during the baseline period
- Vascular disease (defined as myocardial infarction, peripheral artery disease or aortic plaque)
- Frailty (per specific Frailty Score)
- **Comedications**
 - Aspirin
 - P2Y12 Inhibitors
 - Other antiplatelet agents
 - NSAIDs
 - COX-2-specific NSAIDs
 - ACE inhibitors or ARBs

- β -blockers
- Diltiazem
- Verapamil
- Dihydropyridine calcium channel blockers
- Loop diuretic
- Thiazide diuretic
- Digoxin
- Amiodarone
- Dronedarone
- Other antiarrhythmic drugs
- Statins
- Other cholesterol lowering drugs
- Metformin
- Sulfonylureas or glinides
- Thiazolidinediones
- Dipeptidyl peptidase-4 inhibitors
- Glucagon-like peptide-1 agonists
- Insulin
- Benzodiazepines
- SSRIs or SNRIs
- Other antidepressants
- Proton pump inhibitors
- Histamine-2 receptor antagonists
- Systemic corticosteroids
- Exogenous estrogen therapies

- Strong CYP3A4 inhibitors (e.g., protease inhibitors, -azole antifungals)
- Strong CYP3A4 inducers (e.g., phenytoin, carbamazepine, rifampin, St. John's wort)
- Chemotherapy agents (various)
- Laboratory values and vital signs at baseline
 - SBP
 - DBP
 - Hemoglobin
 - D-Dimer
 - Serum creatinine
 - Reported eGFR
 - Height
 - Weight
 - Body mass index (BMI)
 - Platelet count

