- 1.- HES Admitted Patient Care (HES APC) : Complete hospital episode information (admission and discharge dates, diagnoses (identifying primary diagnosis), specialists seen under and procedures undertaken) for each linked patient with a hospitalization record. This is necessary if we do not want to miss any study hospitalized outcome.
- 2.- HES Accident and Emergency (HES A&E) data of patients attending hospitals that may be further be hospitalized. From all information recorded we are specially interest in: A&E diagnosis.
- 3.- Death Registration data contains data from the Office for National Statistics (ONS) and includes information on the official date and causes of death (using ICD codes). This is important to ascertain potential outcomes that may not be in previous sources, but can identify patients dying from the outcome we are studying.

We will request approval to obtain the three linked data sources (HES APC, HES A&E, ONS Death registration) to ascertain all potential study outcome of interest resulting in a hospitalization or being the cause of death. On the other hand we will not request The HES Outpatient (HES OP), as data completeness is an issue in some OP fields and outpatient information may not add relevant clinical information of use for our outcome definitions.

Patients registered in CPRD database are age, sex, and geographically representative of the UK population, and has been extensively validated for use in epidemiological studies [5]. Updated, valid, linked data are available through the CPRD Division of the UK Medicines and Health Care Products Regulatory Agency

Research at the CPRD requires approval from the CPRD Independent Scientific Advisory Committee (ISAC).

The Read classification is used to code specific diagnoses [11, 12] and a drug dictionary based on data from the Gemscript classification is used to record prescriptions [13]. Currently, active patients included in CPRD-GOLD are over 3 million and the corresponding number in Aurum approximates 13 million.

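### The recorded setting of the CAT diagnosis is not among the covariates required in the propensity score, so an imbalance in it could remain in the primary estimates

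*Protocol*

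**What the plan says.** - **Entry (Protocol 9.2.2).** "Cohort entry: CAT diagnosis, hospitalization or emergency department admission or primary care visit with an incident VTE event". Three care settings are therefore part of the cohort definition.
- **Propensity score (9.7).** "All clinical characteristics listed in section 9.3.3 of this protocol will be included in the propensity score model". The sentence appears twice in 9.7.
- **Covariate list (9.3.3).** The list is long and goes down to sleep apnea and osteoarthritis, but it has no item for where the CAT was diagnosed. The two nearest utilization items are "Number of hospitalizations for any cause during the baseline period" and "Number of days between CAT and first recording of anticoagulation use".
- **What weighting can do (9.7).** "overlap weighting cannot adjust for patient characteristics that are not measured and included in the model for the PS".
- **Outcome model (9.7).** "the only independent variable that will be included into Cox regression model will be anticoagulant received".
- **Where setting is used (9.7, sensitivity analyses).** "A sensitivity analysis will be performed whereby patients with cancer will need to be admitted to the hospital, emergency department or observation unit" for the acute event. The reason given is a more contemporary comparison, not control of confounding.
- **Data (9.4).** "We will request approval to obtain the three linked data sources (HES APC, HES A&E, ONS Death registration"; the admitted-care file includes admission and discharge dates. HES Outpatient will not be requested.

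**The concern.** A patient admitted with a pulmonary embolism and a patient whose leg thrombosis is picked up at a GP visit may differ in how ill they are and in who chose the anticoagulant. Section 9.1 says that patients are routinely discharged with a supply of anticoagulant, and that its type, start and amount are not recorded. The first GP record on days 7 to 30 may thus continue a hospital prescription in one patient and be a new GP decision in another. If setting affects both the drug recorded and the outcome, it is a confounder.

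The main analysis adjusts through the propensity score alone, so a variable left out of it is balanced only as far as it correlates with variables that are in it. All three primary outcomes could be affected. Mortality at 3 months is the most exposed, because illness at diagnosis is likely to matter most for early death.

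**Working it through.** **1. Is setting available before exposure?** Yes, as recorded. It is fixed at cohort entry, and the index date defined in 9.2.2 falls 7 to 30 days later. The restricted sensitivity analysis cannot be run without it.

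**2. Is it adjusted for elsewhere?** No. It is absent from 9.3.3, and the Cox model has no covariates.

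**3. The plan's own figures, for scale (9.5).** Person-years: 5,600 × 0.6 = 3,360. Expected events:
- recurrent VTE: 3,360 × 0.118 = 396 (stated 390)
- significant bleeds: 3,360 × 0.144 = 484 (stated 480)
- deaths: 3,360 × 0.80 = 2,688 (stated 2,670)

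Schoenfeld's formula with two-sided 5% (assumed), 80% power, 1:1 allocation and the stated events gives detectable hazard ratios of 0.753, 0.774 and 0.897, against 0.75, 0.77 and 0.89 in the protocol. The figures reproduce closely. They concern first-year events for DOAC versus LMWH, so they serve only as a yardstick.

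**4. Size of a possible bias.** The protocol gives no split by setting and no prognostic effect of setting, so every input here is an assumption. Let p1 and p0 be the proportions hospital-diagnosed in the DOAC and LMWH arms after weighting, and RR the outcome ratio for hospital versus other diagnosis. When the true ratio is 1, the apparent ratio is approximately

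[1 + p1(RR − 1)] / [1 + p0(RR − 1)].

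| p1 | p0 | RR | Calculation | Apparent HR |
|---|---|---|---|---|
| 0.55 | 0.60 | 1.25 | 1.1375/1.15 | 0.99 |
| 0.40 | 0.50 | 1.5 | 1.20/1.25 | 0.96 |
| 0.50 | 0.60 | 2 | 1.50/1.60 | 0.94 |
| 0.50 | 0.70 | 2 | 1.50/1.70 | 0.88 |
| 0.50 | 0.80 | 3 | 2.00/2.60 | 0.77 |

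The result depends on the level of p1 and p0 as well as on the gap. If DOAC patients were the more often hospital-diagnosed, the bias would reverse: 1.70/1.50 = 1.13.

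**5. Can correlated proxies leave a gap?** A simulation of 400,000 patients used a standard normal severity score x, a prior-admission count with mean exp(−0.5 + 0.3x), log-odds of hospital diagnosis 0.4 + 0.3x, and log-odds of DOAC −0.5 − 0.3x − 0.6 × (hospital diagnosis). All these inputs are assumptions.
- Overlap weights from x and the admission count only: 48.7% (DOAC) versus 63.4% (LMWH) hospital-diagnosed.
- Setting added to the logistic model: 53.6% versus 53.6%.

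At RR 2 the first gap gives 1.487/1.634 = 0.91. The second gives 1. This shows the mechanism and does not predict the gap in this cohort.

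**The case against.** The strongest reply has five parts.

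- **The list is a minimum.** Section 9.7 speaks of commonly used variables and accepted risk factors, including other clinical observations, and 9.3.3 introduces its items as examples. A reader might infer that setting is shut out of the model. The text does not support that: it does not require setting, but it does not bar it. What stands is that nothing names it, although much lesser items are named.
- **Partial proxies exist.** Baseline hospitalization count, days from CAT to first anticoagulant record, frailty and metastatic disease will each absorb something. A same-day anticoagulant record may also mark patients started in primary care, since in-hospital drugs are not captured. This stands and pulls the figures towards 1. None of these items identifies the setting, however, and the protocol does not say whether the hospitalization count includes the CAT admission.
- **True setting is not fully known.** A reader might infer that it is known for everyone. It is not. Without HES Outpatient, a clinic diagnosis later coded by the GP could look like a primary care diagnosis. The point therefore concerns recorded setting only.
- **The causal links are not in the protocol.** It does not say that hospital-diagnosed patients are sicker, that the discharge supply reflects a different drug choice, or that setting differs by arm. The delayed start of follow-up and the exclusions for palliative care and for interim bleeding or recurrence also remove some early severity. This stands, so the bias is possible and not shown.
- **The restricted sensitivity analysis helps.** Restriction removes the hospital-versus-primary-care contrast, and comparing it with the main result is informative. It still pools admitted with ED patients, and it leaves the primary estimate unadjusted.

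**Conclusion.** The point holds as a gap in the required adjustment set. A derivable, pre-index variable that defines cohort entry is not required in the propensity score, and no other part of the primary analysis adjusts for it. The protocol does not contradict itself here.

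The effect on the estimates is unknown. Under residual imbalances of 10 to 30 points and risk ratios of 1.5 to 3, at the prevalences tabulated, a null hazard ratio would appear as about 0.96 to 0.77, with less distortion where the listed proxies take up part of the imbalance. Smaller assumptions give 0.99. The direction favours DOACs only if LMWH patients are the more often hospital-diagnosed.

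A reader might infer from the 0.88 row that the expected bias equals the mortality effect the study is sized to detect (0.89). That does not follow: 0.88 requires a 20-point gap remaining after weighting and a doubled risk, and the protocol supports neither figure. The change is still worth making, because the omission is clear and the remedy uses data already being requested.

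**What to change.** 1. Add to section 9.3.3, and so to every propensity model (main, subgroup and matched), the recorded setting of the CAT diagnosis in three levels: admitted, ED only, primary care record.
2. For admitted patients, add length of the index admission up to the index date as defined in 9.2.2, set to 0 for all others. Stopping at the index date keeps it a pre-exposure variable.
3. Report weighted balance on both, by treatment arm. With a logistic model, overlap weighting balances their means exactly; matching does not guarantee this.
4. State in section 9.9 that outpatient-clinic diagnoses may be classed as primary care because HES Outpatient is not requested, so balance on recorded setting may not be balance on true setting.

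Cost: two derived variables from HES files already being requested and a few more model terms. If setting strongly predicts the drug, the effective sample size will be slightly lower. The restricted sensitivity analysis can stay as planned.
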